## 8. MISSING DATA

Under the ITT principle, all patients who are randomized are included in the analysis. Therefore, missing data, especially in the primary outcome measure, can be problematic. All patients randomized will be included in the primary analysis regardless of whether or not they dropped out or discontinued treatment. For the primary analysis, a repeated measures linear mixed model will be fit; this is considered an implicit imputation approach if at least 1 post-baseline assessment is available. However, if baseline is the only assessment available (or if baseline is missing but follow-up available), then a nearest neighbor approach will be used to impute the missing values within aphasia type using age ( $\leq$ ,  $>70$  years), and WAB-R AQ to define “nearest neighbors”.

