#### 9.4.3 Missing Data

The primary analysis will be ITT. All participants randomized will be included in the primary analysis regardless of whether or not they dropped out or discontinued treatment. For the primary analysis, a repeated measures linear mixed model will be fit; this is considered an implicit imputation approach if at least 1 post-baseline assessment is available. However, if baseline is the only assessment available (or if baseline is missing but follow-up available), then a nearest neighbor approach will be used to impute the missing values.

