## Summary of Changes

Version 5; July 2024

- Added Title Page and Summary of Changes.
- Section 7. Clarified that the analyses will adjust for the *centrally scored* baseline WAB-AQ. Updated primary analysis model to include baseline VPM as a covariate to increase efficiency.
- Section 8. Specified variables to use to define nearest neighbors for imputation of missing data.
- Section 11. Updated secondary analysis plan to mixed model approach to account for different timepoints.
- Section 15. Updated exploratory analysis plan to mixed model approach to account for different timepoints.

Version 4; September 2023

- Section 2. Updated “time from stroke onset” to “age at stroke onset” in the list of baseline variables to be compared by treatment group.
- Section 12. Added clearer language describing that the safety monitoring plan includes testing for worsening only of the primary outcome.

Version 3; June 2022

- Section 6. Changed “permuted block design” to “minimization” as minimization is more similar to the hierarchical restrictive covariate adaptive randomization procedure used in SpARc. Clarified that the randomization approach used in SpARc provides a *higher* level of allocation randomness than minimization.
- Section 7. Clarified that the primary outcome is calculated as the change in *average* VPM as VPM is measured on two tasks at each visit. Added the following sentence: “Empirical robust sandwich estimators will be used to account for the randomization procedure in order to appropriately estimate the marginal treatment effect.” Added the EMPIRICAL keyword to the PROC MIXED code. Corrected PROC MIXED syntax to include main effects for arm and visit.
- Section 11. Added individual components of the primary outcome (VPM on Narrative task and Procedural task) as secondary endpoints.
- Section 12. Added new monitoring plan for worsening in the primary outcome.

Version 2; August 2021

- Section 6. Updated the randomization procedure to be used from “asymptotic maximal procedure” to “hierarchical restrictive covariate adaptive randomization procedure” given the small sample size and number of baseline covariates.
- Section 7. Added the following sentence: “As an exploratory analysis, the combined SET duration versus control comparison will be tested at a two-sided alpha of 0.05.”
- References were deleted as the only cited reference was to the asymptotic maximal procedure.

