##### *Sample Size Considerations for Effect Size of SET versus Control group*

For each treatment group versus control we will estimate the standardized mean difference (effect size). The criteria needed to accept any duration is that the effect size is at least 0.36 (a “small” effect size). The rationale for this criteria is that if the pooled standard deviation estimate is large, because of the small sample size, then the effect size may be smaller than expected. We consider a 20% improvement from control to be the MCID. This corresponds to a 1 point improvement in VPM (5x20%=1). Given the MCID=1 and the common SD of change in VPM estimate from pilot data of 2, we expect the effect size to be  $\frac{1}{2}=0.5$ . However, with  $n=20$  per group, observed SD may be as large as 2.74 (i.e. a one-sided upper 95% confidence interval for  $SD=2$  is 2.74), thus the observed effect size may be only  $1/2.74=0.36$ .

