## 7. ANALYSIS OF THE PRIMARY ENDPOINT

The primary outcome is VPM which is a continuous value greater than 0. It is collected at baseline and after 3 months post treatment. The primary analysis will calculate the change in average VPM (from the Narrative Story Telling Task and Procedural Story Telling Task) from baseline. The statistical model will be a repeated measures model (SAS® MIXED procedure with REPEATED subcommand). The model will include the following fixed effects: categorical visit (1 week, 3, and 6 months post treatment period) by treatment group (class variable) interaction, site, baseline aphasia severity score (centrally scored), baseline VPM and age. The estimated difference (95% confidence intervals) in change between each SET duration group and control group will be reported. The standardized mean difference for each SET duration versus control will be used to select the best dose of SET. Since this study is not powered for direct comparison with control, no p-values will be reported.

Empirical robust sandwich estimators will be used to account for the randomization procedure in order to appropriately estimate the marginal treatment effect. The unstructured covariance matrix for repeated observations within subjects will be used. In case the model will not converge, the maximum-likelihood (ML) estimation method will be used instead of the default restricted ML (REML). If the model still does not converge, a simpler covariance structures with less parameters will be used, according to the following order: heterogeneous autoregressive(1) (ARH(1)), heterogeneous compound symmetry (CSH), autoregressive(1) (AR(1)), and compound symmetry (CS). The estimated means at the 3 month post visit of the change from baseline in VPM will be compared for the SET 3 week group versus control, SET 4.5 week versus control, SET 6 week versus control, and the combined SET durations versus control. The SAS code for this analysis is as follows:

```
PROC MIXED EMPIRICAL;
  CLASS SUBJID ARM VISIT CENTER;
  MODEL CHANGE=ARM|VISIT CENTER BASE_WABAQ BASE_VPM AGE;
  REPEATED VISITNUM / TYPE=UN SUBJECT=SUBJID R RCORR;
  LSMEANS ARM*VISIT/ cl;
RUN;
```

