## **9. PRE-SPECIFIED RULE TO SELECT BEST SET DURATION**

- 1- Highest standardized mean difference (effect size) in VPM from baseline to three months post treatment
- 2- Adequate tolerability: group average participation in at least 80% of the treatment sessions

We will select the duration associated with the highest group average VPM at 3 months post treatment, but also had adequate tolerability.

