### **15. EXPLORATORY ANALYSES**

The sensitivity of the treatment effect estimated in the primary analysis may be evaluated with exploratory analyses. The actual values and unadjusted changes from baseline to each visit in primary endpoint will be summarized using descriptive statistics. An exploratory analysis of the primary outcome (VPM) may be conducted as described above for the primary analysis, but including the treatment group assignment as a continuous variable (0, 3, 4.5, 6 weeks). The imputation method of multiple imputation may be explored as a sensitivity analysis.

- Tertiary/Exploratory Endpoints:
  - Communicative Effectiveness Index (CETI)
  - Apraxia of Speech Rating Scale (ASRS)
  - WAB-R

The adjusted mean change from baseline of each SET group will be compared to control with 95% confidence intervals. The statistical model will be a repeated measures model (SAS® MIXED procedure with REPEATED subcommand) including the following fixed effects: categorical visit (1 week, 3, and 6 months post treatment period) by treatment group (class variable) interaction, site, baseline aphasia severity score (centrally scored), baseline value of the exploratory endpoint, and age. In addition, actual values and changes from baseline to each visit in exploratory endpoints will be summarized using descriptive statistics. Since this study is not powered for direct comparison with control, no p-values will be reported.

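### SAP 8 imputes never-assessed participants from neighbours in any arm, so at equal missing fraction f each SET-control difference shrinks to about (1 - f)

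*SAP*

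**What the plan says.** SAP section 8 keeps every randomized participant in the primary analysis. For those with some follow-up it relies on the mixed model: "this is considered an implicit imputation approach if at least 1 post-baseline assessment is available". For those with only a baseline, or with follow-up but no baseline, "then a nearest neighbor approach will be used to impute the missing values within aphasia type using age" group (split at 70 years) and WAB-R AQ. The version 5 entry in the SAP Summary of Changes describes this edit as "Specified variables to use to define nearest neighbors for imputation of missing data", so the list is meant as the specification. Protocol 9.4.3 says only "then a nearest neighbor approach will be used to impute the missing values" and names no variables. Neither document restricts donors to the recipient's arm, and neither says whether VPM or its change is imputed.

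The result feeds the dose decision. SAP section 7: "The standardized mean difference for each SET duration versus control will be used to select the best dose of SET". SAP section 9 puts first "Highest standardized mean difference (effect size) in VPM from baseline to three months post treatment". SAP section 4 adds a bar that section 9 does not repeat: "The criteria needed to accept any duration is that the effect size is at least 0.36". SAP section 11 applies the same missing-data handling to the secondary endpoints. SAP section 15 offers an alternative, but only as an option: "The imputation method of multiple imputation may be explored as a sensitivity analysis".

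**The concern.** An arm-blind donor rule moves outcomes between arms. A control participant who was never assessed is mostly given the outcome of someone who received SET. A never-assessed SET participant is given a control outcome about one time in four. Both pull the groups together.

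It is also at odds with the rest of the analysis. A participant with a single follow-up visit is modelled within their own arm through the arm-by-visit terms in SAP section 7. One with no follow-up visit is filled in across arms.

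At stake are the size of each SET-control difference, the chance that a useful duration reaches 0.36 and, when missingness differs by arm, the relative standing of the durations.

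**Working it through.** **The plan's own figure.** SAP section 4 takes SD 2 and n = 20. The one-sided upper 95% limit is 2 × sqrt(19 / 10.12) = 2.74, and 1/2.74 = 0.36. This reproduces. The bar allows for sampling error in the SD, not for a shrunken numerator.

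**Inputs from the documents.** 80 participants, 1:1:1:1; target difference 1 VPM (protocol 9.2.2); pilot SDs 3.9 before and 4.8 after, and 1.98 for change (protocol 4.3.1), which imply a correlation of (4.8² + 3.9² - 1.98²) / (2 × 4.8 × 3.9) = 0.917.

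**Assumed.** The fraction f with no follow-up VPM at all (5-20% shown); AQ-VPM correlation 0.3; aphasia types 80/15/5%; 25% aged over 70; three equal sites; one donor, nearest on AQ within type and age group. The standardized effect is the adjusted difference over the pooled SD of change.

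**Donor share.** 60/80 = 75% SET; in simulation 73-76% of donors for control dropouts were SET.

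**Formula.** Let mu_k be the true effect of arm k, f_k and f_0 the missing fractions in arm k and control, and m the mean effect in the donor pool. Under missing at random within arm,

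E(diff_k) = (1 - f_k) × mu_k + (f_k - f_0) × m.

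With equal f the second term vanishes and the difference is (1 - f) × mu_k.

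**Equal f, true difference 1.0** (3,000 trials per setting; 3-month ANCOVA of change as a stand-in for the mixed model; donor's change used):

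| f | Formula | Simulated | Standardized effect | Chance of reaching 0.36 |
|---|---|---|---|---|
| no imputation | 1.00 | 1.00-1.02 | about 0.52 | 67-68% |
| 5% | 0.95 | 0.96 | 0.49 | 65% |
| 10% | 0.90 | 0.91 | 0.47 | 63% |
| 20% | 0.80 | 0.79 | 0.41 | 55% |

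A simpler simulation drawing change directly (4,000 trials) gave 0.95, 0.89 and 0.80, and 0.99-1.02 when donors came from the recipient's own arm.

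**Per person, n = 20 per arm.**
- One control missing: 1 - 0.05 × 60/79 = 0.962.
- One SET participant missing: 0.95 + 0.05 × 59/79 = 0.987 for that arm.
- Two controls missing (10%): 1 - 0.10 × 60/78 = 0.923.
- Two missing in one SET arm: 0.90 + 0.10 × 58/78 = 0.974.

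**Unequal f.** True effects 0.25/0.75/1.0 in A/B/C, 20% missing in A and 5% elsewhere. m = (16 × 0.25 + 19 × 0.75 + 19 × 1.0) / 73 = 0.510. Arm A: 0.80 × 0.25 + 0.15 × 0.510 = 0.277 (simulated 0.28). B: 0.95 × 0.75 = 0.71. C: 0.95. The weak dose moves up and the stronger ones down.

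**If the donor's follow-up is set against the recipient's own baseline.** With an exact AQ match and AQ-VPM correlation c, the SD of that person's change is sqrt(4.8² + 3.9² - 2 × c² × 4.8 × 3.9): 6.18, 5.91, 5.37 and 3.78 for c = 0, 0.3, 0.5 and 0.8, against 1.98. At 10% missing the standardized effect is then about 0.35-0.36 for c from 0 to 0.3, 0.37 for 0.5 and 0.41 for 0.8.

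**Missing baseline.** The raw difference is not biased (1.01-1.02 simulated). Setting a donor's baseline against own follow-up at 5% and 10% missing raises the pooled SD of change to 2.31 and 2.61 and lowers the standardized effect to 0.45 and 0.40.

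**The case against.** - **The trigger is narrow.** It needs no VPM at any of three visits. Failed testing is repeated (protocol Table 1 note), discontinuers are pursued for the primary outcome (7.1) and losses are expected to be few (7.3). With 20 per arm, 5% is one person. At 5-10% the shift is about 0.1 to 0.2 of the sampling error of the standardized effect (about 0.33). This stands and limits the size.
- **Dose order is hardly touched.** Control missingness enters every raw difference as the same term, -f_0 × m, and the closing sentence of SAP section 9 ranks arms by group average VPM, where control does not enter. The unequal example also keeps its order. This stands for the ranking; the 0.36 bar and the reported differences remain affected.
- **Shrinkage may be right if never-assessed SET participants gained nothing.** At equal f, the no-gain truth is indeed (1 - f). But with 10% missing only in control the truth is 1.0 on either view and the rule gives 0.92. With 10% missing only in one SET arm, the no-gain truth is 0.90 and the rule gives 0.97. Multiple imputation with arm in the model would give about 1.00 there, further off, so a sensitivity analysis should accompany it.
- **The biased rule can have lower overall error.** At 10% missing its SD is 0.62 with bias 0.09-0.10, so root mean square error is sqrt(0.62² + 0.10²) = 0.63, against about 0.65-0.67 for multiple imputation. The arithmetic stands, but it does not justify crediting control participants with SET gains.
- **The mismatched-donor figures rest on one reading.** SAP section 8 neither states nor excludes it. They show that the text must be settled, not what will happen.

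**Conclusion.** The concern holds. As written, the rule fills in never-assessed participants across arms and biases each SET-control difference toward zero by about the missing fraction when that fraction is equal: roughly 0.05 VPM at 5%, 0.10 at 10% and 0.20 at 20% of a true 1.0. This rests on missing at random within arm, which the mixed model already assumes, and on reading the listed variables as the full specification. The rate is unknown and probably low, so the practical effect may be small. The bias is systematic and avoidable, though, and it falls on the quantity used to judge and select a duration. It should be fixed, with medium confidence in how much it will matter.

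**What to change.** In SAP section 8 and protocol 9.4.3, replace the nearest-neighbour rule with the multiple imputation that SAP section 15 now leaves optional. Suggested text:

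> Participants with no follow-up VPM or no baseline VPM are handled by multiple imputation of VPM (not change) from arm, site, age, WAB-R AQ and all observed VPM values, combined with Rubin's rules.

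Add one sensitivity analysis in which never-assessed SET participants are given control-like change. The primary change model stays as it is.

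In simulation (2,000 trials per setting) this gave mean differences of 0.98-1.02 and interval coverage of 93.4%, 92.9% and 94.0% at 5%, 10% and 20% missing, against 93.3% with complete data. Simply restricting a single donor to the recipient's arm also removes the bias (1.00-1.02), but it treats imputed values as observed: coverage is 92.4%, 90.5% and 87.0%. With 20 per arm it would also need a fallback where no donor matches on type and age group.

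The cost is wording in two places and modest programming. Intervals widen slightly: at 10% missing the SD of the estimate is about 0.65-0.67, against 0.62 under the arm-blind rule using donor change.

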## **9. PRE-SPECIFIED RULE TO SELECT BEST SET DURATION**

- 1- Highest standardized mean difference (effect size) in VPM from baseline to three months post treatment
- 2- Adequate tolerability: group average participation in at least 80% of the treatment sessions

We will select the duration associated with the highest group average VPM at 3 months post treatment, but also had adequate tolerability.

## **10. TOLERABILITY**

For each participant, the participation rate will be calculated as the number of completed treatment sessions divided by the expected number of treatment sessions (with allowances for out of window sessions). The average participation rate (95% confidence intervals) will be calculated for each treatment group. Adequate tolerability of a SET duration would be having a group average participation in at least 80% of the treatment sessions.

## **11. ANALYSIS OF THE SECONDARY ENDPOINTS**

- Secondary Endpoint(s):
  - Quality of life assessment - SAQOL-39
  - Individual components of the primary outcome:
    - VPM on Narrative Story Telling Task
    - VPM on Procedural Story Telling Task

The secondary endpoints will be analyzed similarly to the primary endpoint. The same approach will be used to define the analysis sample and handling of missing data. The adjusted mean change from baseline of each SET group will be compared to control with 95% confidence intervals. The statistical model will be a repeated measures model (SAS® MIXED procedure with REPEATED subcommand) including the following fixed effects: categorical visit (1 week, 3, and 6 months post treatment period) by treatment group (class variable) interaction, site, baseline aphasia severity score (centrally scored), baseline value of the secondary endpoint, and age.

In addition, actual values and changes from baseline to each visit in secondary endpoints will be summarized using descriptive statistics. Since this study is not powered for direct comparison with control, no p-values will be reported.

## **12. SAFETY ANALYSES**

### **Monitoring Plan for Worsening in the Primary Outcome**

If SET leads to substantially worse outcome than the no SET arm, early stopping may be considered. The unblinded statistician will fit the primary analysis model semi-annually in order to compare VPM between the combined SET durations versus No SET to detect worsening only (one-sided  $\alpha=0.025$ ). As part of this analysis, outliers will be explored to ensure that the results are not driven by a specific

individual. Should the null hypothesis be rejected, an investigation of dose response among the SET arms based on qualitative evaluation (i.e. not statistical) when ordered in terms of dose level will occur. Should a dose response worsening be detected, the unblinded statistician will bring this to the attention of the DSMB and investigators.

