#### 9.4.6 Safety Analyses

Monitoring Plan for Worsening in the Primary Outcome: If SET leads to substantially worse outcome than the no SET arm, early stopping may be considered. The unblinded statistician will fit the primary analysis model semi-annually in order to compare VPM between the combined SET durations versus No SET (one-sided  $\alpha$ =0.025). As part of this analysis, outliers will be explored to ensure that the results are not driven by a specific individual. Should the null hypothesis be rejected, an investigation of dose response among the SET arms based on qualitative evaluation (i.e. not statistical) when ordered in terms of dose level will occur. Should a dose response relationship be detected, the unblinded statistician will bring this to the attention of the DSMB and investigators.

All AEs and SAEs are summarized by preferred term according to the Medical Dictionary for Regulatory Activities (MedDRA) adverse reaction dictionary in terms of frequency of the event, number of subjects having the event. For the Closed DSMB report, severity, and relatedness to the treatment will also be shown by treatment group.

At the end of the trial, the cumulative incidences of the specific SAEs related to treatment, as well as all SAEs, will be compared across groups.

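### VPM harm is examined by duration only after a pooled SET-versus-control test rejects, so worsening concentrated in the longest duration is cut to one third and usually missed

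*SAP*

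**What the plan says.** SAP 12 (Monitoring Plan for Worsening in the Primary Outcome) sets one formal harm test on VPM. Every six months the primary model is refitted by the unblinded statistician to "compare VPM between the combined SET durations versus No SET to detect worsening only", at one-sided alpha 0.025. Protocol 9.4.6 describes the same one-sided comparison: "compare VPM between the combined SET durations versus No SET".

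The look by duration depends on that result: "Should the null hypothesis be rejected, an investigation of dose response among the SET arms based on qualitative evaluation". Escalation is a further step: "Should a dose response worsening be detected, the unblinded statistician will bring this to the attention of the DSMB and investigators".

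Three other places bear on the point:
- SAP 12 (Safety Monitoring) provides closed DSMB tables by partially blinded group, but the content it specifies is serious adverse events, not VPM.
- The SAS code in SAP 7 prints adjusted means by arm and visit, so the unblinded statistician will hold estimates for each duration. No written rule acts on them unless the pooled test rejects.
- SAP 15 allows an optional end-of-trial model "including the treatment group assignment as a continuous variable (0, 3, 4.5, 6 weeks"). A dose coding therefore already exists, but it is not used in monitoring.

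**The concern.** The trial is run because effect is expected to vary with duration, and the last step of the harm rule looks for worsening related to dose. Yet the test that must reject first averages over dose. If harm sits in one arm, the other two arms dilute it. If a shorter duration helps, its benefit offsets the harm. The 3-week pilot mean gain was 1.11 VPM (Protocol 4.3.1).

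At stake is how a quiet monitoring report is read. The DSMB could take the absence of a signal as reassurance about every duration, when the test had little chance of reacting to harm in the longest one.

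**Working it through.** **Inputs from the documents.** Four arms at 1:1:1:1 and 80 in total, so 20 per arm (SAP 1). SD of change 2, upper value 2.74, MCID 1 VPM (SAP 4). One-sided alpha 0.025 (SAP 12). Dose coding 0, 3, 4.5, 6 weeks (SAP 15).

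**Assumptions.** The documents give no harm size, harm shape or power for this rule. I take a worst-arm harm of 1 VPM (the MCID) and 2 VPM, the shapes listed below, no dropout, no gain from covariates, and a normal approximation. A noncentral t with 76 df changes no power at 20 per arm by more than about 1 point.

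**The plan's own nearest figure.** Upper limit for the SD: 2 × √(19 / χ²(0.05, 19 df)) = 2.74. Effect size: 1 / 2.74 = 0.365, which the plan gives as 0.36. Both are reproduced.

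**Contrasts and standard errors (SD 2, 20 per arm).**
- Pooled: mean of the three SET arms minus control; SE = 2 × √(1/60 + 1/20) = 0.516.
- Linear trend: centred weeks (−3.375, −0.375, 1.125, 2.625), sum of squares 19.69; SE = 2 × √(19.69/20) = 1.984.
- 6 weeks versus control: SE = 2 × √(2/20) = 0.632.

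Chance of a signal = Φ(contrast / SE − 1.96).

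**Harm in the 6-week arm only.** The pooled contrast is δ/3.
- Pooled: 0.333/0.516 − 1.96 = −1.31, so 9% at 1 VPM; 0.667/0.516 − 1.96 = −0.67, so 25% at 2 VPM.
- Trend: 2.625/1.984 − 1.96 = −0.64, so 26%; 5.25/1.984 − 1.96 = 0.69, so 75%.
- 6 weeks versus control: 1/0.632 − 1.96 = −0.38, so 35%; 2/0.632 − 1.96 = 1.20, so 89%.

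The 6-week harm needed for 80% power is 4.34 VPM (pooled), 2.12 (trend) and 1.77 (6 weeks versus control).

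**Other shapes.** Entries are the chance of a signal at a worst-arm harm of 1 / 2 VPM.

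| Harm at 3 / 4.5 / 6 weeks, as a share of the worst | Share left after pooling | Pooled | Trend |
|---|---|---|---|
| 0 / 0 / 1 | 1/3 | 9% / 25% | 26% / 75% |
| 0 / 0.5 / 1 | 1/2 | 16% / 49% | 36% / 89% |
| 0.5 / 0.75 / 1 (proportional to weeks) | 3/4 | 31% / 83% | 38% / 91% |
| 1 / 1 / 1 (flat) | 1 | 49% / 97% | 40% / 93% |
| 0 / 1 / 0 | 1/3 | 9% / 25% | 8% / 20% |
| 1 / 0 / 0 | 1/3 | 9% / 25% | 2% / 1% |

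**Offsetting benefit.** Take 2 VPM harm at 6 weeks and none at 4.5. A 3-week benefit of 0.3 SD (0.6 VPM) leaves a pooled contrast of (2 − 0.6)/3 = 0.467: pooled 15%, trend 79%. A benefit of the pilot size leaves (2 − 1.11)/3 = 0.297: pooled 8%, trend 82%.

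**Earlier in the trial and with a larger SD (6-week-only harm, 1 / 2 VPM).** At 10 per arm, SD 2: pooled 7% / 15%, trend 15% / 46%. At 20 per arm, SD 2.74: pooled 7% / 15%, trend 16% / 49%.

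**Price of a second trigger.** The correlation between the pooled and trend contrasts is 4.5 / (√1.333 × √19.69) = 0.88. Under no effect, the chance that either rejects at one look is about 3.6%, against 2.5% for the pooled test alone. Over four assumed equal looks with no adjustment it is about 9%, against about 6%.

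**The case against.** The rule targets SET being substantially worse than no SET. Pooling 60 against 20 is a coherent choice for that in a trial not powered for single-duration comparisons. It is the best of these tests for flat harm. That stands, and it is why the pooled contrast should be kept.

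A reader might infer that the rule is weakest against dose-related worsening in general. The figures do not support this. Harm proportional to weeks keeps three quarters of its size, and the trend test then gains only about 7 to 8 points. Harm confined to 3 or 4.5 weeks is diluted just as much. The loss comes from concentration in one arm, and the trend contrast does not help when that arm is a shorter duration.

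A reader might also infer that the statistician would hold data plainly showing the harm while enrolment goes on. The 75% and 89% figures need 3-month data on all 80 participants. At 10 per arm the trend test reaches 46% at 2 VPM and 15% at 1 VPM. Even at full size it misses most harm of 1 VPM.

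Harm only at 6 weeks is not what earlier data suggest. Protocol 2.2.8 reports more words produced and a near-significant VPM gain after 6 weeks of daily SET in 13 people. Protocol 2.3.3 names occasional fatigue as the only reaction to treatment. That study was small, and a monitoring rule is there for the unexpected, so this lowers the urgency without removing the gap.

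Finally, estimates by arm are produced at each run, and the DSMB may request reports. This narrows the gap, but nothing in the plan requires VPM by duration to be shown.

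**Conclusion.** The point holds for worsening concentrated in the longest duration. The pooled gate reduces it to exactly one third when the arms are equal and the other two durations have no effect, and it would open 9% to 25% of the time for harm of 1 to 2 VPM at full enrolment (SD 2). Benefit at a shorter duration lowers this further. The loss is modest for harm graded with weeks, and for flat harm the pooled test is the better one.

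The one-third figure follows from the design. The percentages rest on assumed harm sizes and shapes, no dropout and no covariate gain. The point concerns a monitoring rule that opens a review. It does not affect the primary estimates, and it is no evidence that any duration is harmful. The change is worth making because it is cheap.

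**What to change.** In SAP 12 and Protocol 9.4.6, at each semi-annual run of the same fitted model:
1. Keep the pooled contrast as it is.
2. Show each SET duration versus No SET at 3 months, with its 95% CI, in the closed DSMB report whether or not the pooled test rejects. This is the core of the change: it uses no alpha and is the only part that brings out harm confined to 3 weeks.
3. Add a one-sided linear dose contrast at 3 months over 0, 3, 4.5 and 6 weeks, the coding already in SAP 15, and let either contrast open the review by duration.

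**Cost.** A few ESTIMATE statements and a sentence or two in each document. The false-alarm rate per look rises from 2.5% to about 3.6%, and more over repeated looks. The SAP should state that these looks are unadjusted. A false alarm leads to a qualitative review and not to an automatic stop.
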